5.4.3 General principles for management of toxicity with combination therapy

The combinations of cabozantinib and immunotherapy are still investigational, and unanticipated or synergistic side effects may be observed. Toxicity from combination therapy may be difficult to attribute to cabozantinib versus nivolumab (with or without ipilimumab). Guidance is provided below in defining attribution by holding cabozantinib, or by empirically starting corticosteroids.

As a general approach, it is suggested that AEs be treated with supportive care when possible at the earliest signs of toxicity. The below management guidelines are provided based on what is known individually about cabozantinib and nivolumab/ipilimumab, with additional guidance in the areas of overlap. They are not mandatory and investigator discretion may be used.

There are many circumstances in which the instructions below dictate permanent discontinuation of therapy. If an investigator feels that it is in the patient's best interest to continue on study therapy, study chair approval may be obtained prior to restarting drug.

Table of relative likelihood of cabozantinib-related and immune-related toxicities.

++ More common

+ Less common

- Infrequent

Toxicity	Cabozantinib-related	Immune-related	Protocol management section
Diarrhea	++	++	5.4.6
Nausea and Vomiting	++	+	5.4.7
Oral mucositis	++	-	5.4.8
Hand-foot syndrome (palmar-plantar erythrodysesthesia syndrome)	++	-	5.4.8
Skin Rash	+	+	5.4.8
Transaminitis (AST/ALT increased)	+	++	5.4.9
Hyperbilirubinemia (bilirubin increased)	-	+	5.4.9
Amylase/lipase increased; pancreatitis	+	-	5.4.9
Pneumonitis	+	++	5.4.10
Hypothyroidism	++	++	5.4.11
Adrenal insufficiency	-	+	5.4.11
Neurologic events	-	+	5.4.12
Renal dysfunction	-	-	5.4.13
Proteinuria	+	-	5.4.13
Fatigue	++	++	5.4.14
Fever	-	-	5.4.15
Infusion reaction	N/A	-	5.4.16
Thrombosis/embolism	+	-	5.4.17
Hypertension	++	-	5.4.18
Cardiomyopathy/myocarditis	-	+	5.4.19
Hemorrhagic events	+	-	5.4.20
Fistula formation/perforation	+	-	5.4.21
Wound healing problems	+	-	5.4.22
Osteonecrosis of the jaw	+	-	5.4.23
Cardiac QTc prolongation	+	-	5.4.24

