5.4.5 Immune-related adverse events

Immune-related adverse events can happen with any onset in relationship to immune therapy administration, even months after discontinuation of therapy. Corticosteroids are the mainstay of therapy for immune-related adverse events. Most should improve or resolve with an adequate dose of steroids. Prior to starting corticosteroids or hormone replacement for any reason, appropriate endocrine testing including cortisol, ACTH, TSH and reflex T4 to document baseline is strongly recommended.

Please note that in some cases the treatment algorithms recommend steroids if symptoms do not resolve in 7 days. However, this recommendation is not meant to delay steroid treatment at any time it is clinically indicated. Any patient started on corticosteroids initially who is determined to not require steroid treatment for an autoimmune adverse event may resume therapy after an observation period without further symptoms at the discretion of the investigator. Any patients who require additional immune suppressive treatment beyond steroids should go off immune therapy study treatment (but may continue cabozantinib as appropriate).

If AE's are felt to be immune related and drugs are held, nivolumab and ipilimumab should either be given together or both held. Cabozantinib may be either continued, or held, as felt appropriate by the investigator depending on the particular toxicity. The study chair may be contacted for individual circumstances to provide additional guidance.

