5.4.10 Pneumonitis

[figure not shown]
Management of cabozantinib associated pneumonitis

Pneumonitis has been associated with cabozantinib, nivolumab, and ipilimumab therapies individually. In general it is difficult to definitively diagnose and can be life threatening. Patients with proven symptomatic clinically proven pneumonitis refractory to management guidelines for nivolumab +/- ipilimumab (below) should have cabozantinib permanently discontinued, if they were on cabozantinib therapy.

Pneumonitis	Management/Next Dose for Nivolumab+/-Ipilimumab
≤ Grade 1	Hold dose pending evaluation and resolution to baseline including baseline pO2. Resume no change in dose after pulmonary and/or ID consultation excludes lymphocytic pneumonitis.
Grade 2	Hold dose pending evaluation. Resume no change in dose after pulmonary and/or ID consultation excludes ipilimumab and associated lymphocytic pneumonitis as the cause of the pneumonitis. Off study if steroids are required. ^
Grade 3	Hold dose pending evaluation. Resume no change in dose after pulmonary and/or ID consultation excludes ipilimumab and associated lymphocytic pneumonitis as the cause of the pneumonitis. Off study if steroids are required
Grade 4	Off protocol therapy
Distinguishing inflammatory pneumonitis is often a diagnosis of exclusion for patients who do not respond to antibiotics and have no causal organism identified including influenza. Most patients with respiratory failure or hypoxia will be treated with steroids. Bronchoscopy may be required and analysis of lavage fluid for lymphocytic predominance may be helpful. Patients with new lung nodules should be evaluated for sarcoid like granuloma. Please consider recommending seasonal influenza killed vaccine for all patients.	
Recommended management: See Pulmonary Adverse Event Management Algorithm	

Pulmonary Adverse Event Management Algorithm

Rule out non-inflammatory causes. If non-inflammatory cause, treat accordingly and continue I-O therapy. Evaluate with imaging and pulmonary consultation.

Patients on IV steroids may be switched to an equivalent dose of oral corticosteroids (e.g. prednisone) at start of tapering or earlier, once sustained clinical improvement is observed. Lower bioavailability of oral corticosteroids should be taken into account when switching to the equivalent dose of oral corticosteroids.

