9.3 Statistical Analysis Plan

The primary and some secondary analyses will include all eligible and treated patients. Exceptions to this include: analysis of toxicity data, which will include all patients who received study drug regardless of eligibility, and analyses of response, which will include eligible and treated patients with measurable and evaluable disease.

Time-to-event data, such as PFS and OS, will be estimated using the Kaplan-Meier method, and Cox proportional hazards models will be used to estimate the treatment hazard ratios. The primary comparison of PFS will use a logrank test stratified on the randomization stratification factors with a one-sided type I error rate of 10%. Other comparisons of groups will be made using the logrank test and Cox modeling.

Categorical data, such as response rates (CR+PR) and toxicity, will be compared using Fisher's exact tests with a one-sided type I error rate of 10%; multivariable logistic regression modeling will be used to adjust for the effect of any covariates that are associated with these categorical outcomes. Though none are currently planned, any continuous outcomes will be analyzed using Wilcoxon rank sum test, and multivariable linear regression models may be used to adjust for multiple associations with outcome.

Modeling procedures will implement backward selection; variables significant at the 0.10 level in the univariate setting will be chosen for inclusion in an initial full model, and at each step the least significant variable will be removed from the model. Only those covariates with $p < 0.05$ will remain in any final models, unless there are factors identified by the study team as crucial to model interpretation.

Point estimates of all endpoints will be accompanied by the corresponding two-sided 80% confidence intervals.

In the event that there are missing data, no imputation of the missing data will be conducted. We will assume that data are missing at random and will conduct all analyses as originally planned because we do not anticipate an excess of missing data.

Subset analyses are planned for all stratification factors and all known prognostic factors, such as performance status, age, sites of metastases, gender, etc. Subset analyses of all variables, including correlatives, are considered to be exploratory in nature.

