9.8.2 Interim Analysis: Safety Monitoring

Interim analyses of toxicity are performed twice yearly for all ECOG-ACRIN studies. Reports of these analyses are sent to the ECOG-ACRIN Principal Investigator or Senior Investigator at the participating institutions. Expedited reporting of certain adverse events is required, as described in Section [5.2](#).

Because this is the first time that ipilimumab is being combined with nivolumab and cabozantinib in this population, close monitoring of toxicity is an important endpoint of the trial. We will collect data and conduct an interim safety analysis among the first 15 patients who have completed the first two cycles of treatment on each arm. This will be done without a planned suspension to accrual. The safety analysis will be done based on the case report form database and the CTEP-AERS database, although the focus will largely be placed on the CTEP-AERS data. The safety data will be reviewed with the sponsor (CTEP) to rule out the incidence of excessive toxicities. This preliminary toxicity analysis will occur in addition to the twice yearly monitoring for toxicity for the purposes of interim reporting.

In particular, there is concern for excessive rates of pneumonitis or colitis on the 3-drug regimen. With respect to colitis, prior studies have demonstrated that grade 3-5 colitis occurs in approximately 11% of patients with nivolumab and ipilimumab therapy. As such, if we observe 5 or more patients with grade 3-5 treatment-related colitis among 15 patients analyzed per arm, the lower bound of the two-sided 90% exact binomial confidence interval will have exceeded 11% and consideration may be given to terminating the arm associated with the higher rate of colitis.

With respect to pneumonitis, a similar approach will be used. Prior studies have demonstrated that grade 3-5 pneumonitis occurs in approximately 3% of patients treated with nivolumab and ipilimumab. Therefore, if we observe 3 or more grade 3-5 incidents of treatment-related pneumonitis in a cohort of 15 patients, then the lower bound of the two-sided 90% exact binomial confidence interval will have exceeded 3% and consideration may be given to terminating the arm associated with the higher rate of pneumonitis.

10. Specimen Submissions

Tumor tissue specimens must be submitted for defined laboratory research studies described in Section [11](#).

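### Section 9.8.2 should define its 15-patient safety cohort from first dose and prompt the CTEP review when the colitis or pneumonitis count is reached

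*Combined protocol and SAP*

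**What the plan says.** Section 9.8.2 plans an "interim safety analysis among the first 15 patients who have completed the first two cycles of treatment on each arm". Of accrual it says: "This will be done without a planned suspension to accrual". The look draws mainly on CTEP-AERS and is reviewed with CTEP.

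The colitis criterion applies "if we observe 5 or more patients with grade 3-5 treatment-related colitis among 15 patients analyzed per arm", against a reference rate of 11%. The pneumonitis criterion is 3 or more of 15, against 3%, and is worded in incidents rather than patients. Both are advisory: consideration may be given to terminating the arm.

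Four other places bear on this.
- Section 9.8.2 also schedules toxicity analyses twice a year, in addition to this look, with no count attached.
- Section 5.2.10 requires each treatment-related grade 3-5 colitis or pneumonitis to be reported in CTEP-AERS within 24 hours.
- Section 9.3 describes "analysis of toxicity data, which will include all patients who received study drug regardless of eligibility".
- Section 5.4.10 says of grade 3 pneumonitis: "Off study if steroids are required". Grade 4 goes off protocol therapy. Section 5.4.3 says of the management guidelines: "They are not mandatory and investigator discretion may be used".

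**The concern.** **Cohort.** If only patients who complete two cycles enter the 15, a patient who dies of pneumonitis in cycle 1 cannot be counted. A patient taken off treatment for grade 3-4 pneumonitis may not be counted either. These are the events the rule was written to detect. Section 9.3 points to a wider population, but 9.8.2 does not say which reading governs.

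**Timing.** The data that would show an arm at its count are in CTEP-AERS within a day of each case becoming known. Yet 9.8.2 names no count that calls for a review before the look, and accrual stays open. What is at stake is a modest number of further patients starting on an arm that has already met the plan's own criterion.

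**Working it through.** **1. The plan's thresholds reproduce.** The lower limit of a two-sided 90% exact interval for x of 15 is the 5% quantile of Beta(x, 16 - x).
- Colitis: 4 cases give 9.7%, 5 give 14.2%. Five is the smallest count above 11%.
- Pneumonitis: 2 cases give 2.4%, 3 give 5.7%. Three is the smallest count above 3%.

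**2. Chance of reaching the count** among 15 treated patients (binomial tail, every event observed):

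| Count | True rate: probability |
|---|---|
| 5 or more colitis | 11%: 0.019; 20%: 0.164; 30%: 0.485 |
| 3 or more pneumonitis | 3%: 0.009; 10%: 0.184; 20%: 0.602; 30%: 0.873 |

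**3. Literal two-cycle cohort, pneumonitis.** Let p be the true rate, and q and u the shares of affected and unaffected patients left out. The rate in the cohort is p(1-q) / [p(1-q) + (1-p)(1-u)]. The documents give neither q nor u. I take q = 0.25 or 0.5. For u I take 0 to 0.16; the upper value uses the combination-arm PFS hazard in Section 9.4 over 56 days: 1 - exp(-0.096 x 56/30.44) = 16.2%.
- p = 20%, q = 0.25: cohort rate 15.8% to 18.2%; chance of 3 of 15 is 43-53%, against 60%.
- p = 20%, q = 0.5: 11.1% to 13.0%; chance 23-31%.
- p = 30%: chance 75-83% (q = 0.25) and 51-61% (q = 0.5), against 87%.
- p = 20%, q = 0, u = 0.16: chance 70%. Here the literal cohort raises it.

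The two definitions agree when q = u, so the direction turns on which group drops out more.

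**4. Timing.** The assumptions below are not in the plan.
- Accrual: 144 randomized / 3 arms / 15 months (Sections 9.4 and 9.5) = 3.2 per arm per month, arriving at random.
- Look: when the 15th treated patient reaches day 56, at about 15/3.2 + 56/30.44 = 4.7 + 1.8 = 6.5 months.
- Onset: uniform over days 0-56, 28-56, 0-112 or 0-168. The long ranges are there because Section 5.4.5 says: "Immune-related adverse events can happen with any onset in relationship to immune therapy administration, even months after discontinuation of therapy".
- Twice-yearly analyses: every 6 months at a random phase, each treated as a review that would notice the count.

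The wait runs from the event that completes the count to the look or the next twice-yearly analysis, whichever is first. Further patients = 3.2 x wait. Ranges from simulation, across the four onset assumptions:

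| Setting | Mean wait if count reached, look only | With twice-yearly analyses | Expected further patients over all arms, with twice-yearly |
|---|---|---|---|
| Colitis 30% | 1.1-1.9 months | 0.9-1.5 months | 0.6-2.3 |
| Pneumonitis 20% | 1.5-2.4 months | 1.2-1.8 months | 1.4-3.5 |

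The last column includes arms that never reach the count. For colitis with onset over days 0-56: 0.485 x 3.2 x 1.5 = 2.3. At 20% colitis the expected number is at most 0.9, and at 10% pneumonitis at most 1.2, even before allowing for the twice-yearly analyses. At the reference rates it is 0.1 or less.

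**5. The count must close at the look.** With late onset, a count left open is reached more often than one closed at the look. For 30% colitis the figures are 48% against 35% (0-112 days) and 48% against 19% (0-168 days). For 20% pneumonitis they are 60% against 50% and 60% against 35%. With a first-15-treated cohort and closure at the look, reviewing sooner leaves the chance of reaching the count unchanged, because a reported count only accumulates.

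**The case against.** The case against has several parts, and much of it stands.
- **Reviews before the look exist.** A reader might infer that an arm reaching its count early has no planned review until the look. That is not so: twice-yearly toxicity analyses are planned, and one will usually fall before 6.5 months. CTEP also holds every report within 24 hours and can act at any time. The main figures therefore include the twice-yearly analyses. What remains missing is a stated count that prompts a review.
- **The cohort wording may only time the look.** Section 9.3 favours counting everyone who received drug. The management tables are not mandatory, and the 5.4.10 table concerns nivolumab and ipilimumab, so a patient might continue cabozantinib. The left-out shares are assumed. This reduces the point to an ambiguity, but a death before two cycles is outside the literal cohort whatever the investigator's discretion.
- **Colitis.** A reader might extend the cohort argument to colitis. Section 5.4.6 allows rechallenge after grade 3 diarrhea, and no comparable route out of treatment is shown.
- **The rates are high.** The larger gains need about three times the colitis reference rate (30/11) and seven times the pneumonitis one (20/3). The only triplet data in the document (Section 1.2, genitourinary tumors) show grade 3 colitis in 1 of 18, with pneumonitis not listed.
- **Completing two cycles secures exposure.** At the Section 9.4 hazards, 16-27% of treated patients progress or die by day 56. If risk ended with treatment, 20% pneumonitis would reach 3 of 15 in about 49-54% of arms rather than 60%. This is a genuine trade-off.
- **Practical benefit.** Responses to CTEP's comments, at the front of the document, describe the study as suspended and likely to be terminated for slow accrual.

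**Conclusion.** The point holds in a limited form and is worth considering because it is cheap. The thresholds are arithmetically right and need no change. There are two gaps: the cohort is ambiguous for patients who stop early, and no count prompts a review before the look.

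One might read the literal cohort as certain to hide an excess of pneumonitis. The documents do not support that. It is one reading, its size rests on assumed shares, and it reverses if unaffected patients drop out more often than affected ones.

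When the count is reached, the timing gain is about 0.9-1.5 months at 30% colitis and 1.2-1.8 months at 20% pneumonitis, with little effect near the reference rates. These figures rest on the assumed accrual, onset ranges and random phase of the twice-yearly analyses. The rule stays advisory, so the gain is a clear cohort and a stated time for review, not a new power to stop.

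**What to change.** In Section 9.8.2:
1. Define the cohort as the first 15 patients who start treatment on each arm, including those who stop before completing two cycles, and hold the look when the 15th reaches day 56.
2. Hold the CTEP review as soon as the 5th patient with treatment-related grade 3-5 colitis, or the 3rd with treatment-related grade 3-5 pneumonitis, is reported in that cohort. State that patients, not incidents, are counted and that the count closes at the look; later events stay under the twice-yearly monitoring.
3. Keep the scheduled look for arms that have not reached a count.

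The cost is two or three sentences and a running tally of reports already received, with no added patients and no new committee. With every event observed by the look, the chance of reaching a count at the reference rates stays at 0.019 and 0.009. There are two downsides. An occasional ad hoc review would use uncleaned data, and attribution may later change: "Toxicity from combination therapy may be difficult to attribute", as Section 5.4.3 says. Some of the 15 will also have short exposure because of early progression, so the look should report time on treatment beside the counts.

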10.1.1 Pathological Material Submission

Representative tumor tissue specimens are to be submitted for defined laboratory research studies within one month of randomization.

Submitting pathologist and clinical research associate may refer to [Appendix I](#) which outlines the Pathology Submission Guidelines.

The tumor tissue specimens are to be labeled with the institution's assigned pathology ID# as well as the information above.

10.1.1.1 Required Materials

Forms: Must be submitted with all pathology submissions.

- STS generated shipping manifest form
- Copy of the institutional pathology report
- Immunological study reports, if available

Tumor Tissue Submission:

- Formalin-fixed paraffin-embedded (FFPE) tumor tissue block

NOTE: If blocks are unavailable for submission, cores and slides are to be submitted. All cores and slides must be adequately labeled, with slides numbered sequentially in the order cut.

Alternative submission requirements:

- One (1) H&E slide
- Twenty (20) 5 μ m unstained, uncharged, air-dried plus slides from the thickest part of the tumor
- One (1) or more core punches (minimum of 4mm diameter). If core punch tool is unavailable, request core punch kit from the ECOG-ACRIN CBPF [contact].

Adequately label every slide and core submitted.

If these criteria cannot be met, please contact the ECOG-ACRIN CBPF ([contact]) to obtain alternative submission requirements.

10.1.2 Shipping Procedures

Pathology materials are to be shipped at ambient temperature within one month following randomization.

Ship using the CBPF's FedEx account using the FedEx on-line ship manager.

Ship to:

ECOG-ACRIN Central Biorepository and Pathology Facility
MD Anderson Cancer Center
Department of Pathology, Unit 085
Tissue Qualification Laboratory for ECOG-ACRIN, Room G1.3586
[name]
[name]
Phone: Toll Free [contact] [contact] Local or International Sites)
[contact]
Email: [contact]

Access to the FedEx shipping account for shipments to the ECOG-ACRIN CBPF at MD Anderson Cancer Center can only be obtained by logging onto fedex.com with an account issued by the ECOG-ACRIN CBPF. For security reasons, the account number will no longer be given out in protocols, over the phone, or via email. If your site needs to have an account created, please contact the ECOG-ACRIN CBPF by email at [contact]

An STS shipping manifest form must be generated and shipped with all specimen submissions.

10.2 ECOG-ACRIN Sample Tracking System

It is **required** that all specimens submitted on this trial be entered and tracked using the ECOG-ACRIN Sample Tracking System (STS). The software will allow the use of either 1) an ECOG-ACRIN user-name and password previously assigned (for those already using STS), or 2) a CTSU username and password.

When you are ready to log the collection and/or shipment of the specimens required for this study, please access the Sample Tracking System software by clicking <https://webapps.ecog.org/Tst>

Important: Please note that the STS software creates pop-up windows, so you will need to enable pop-ups within your web browser while using the software. A user manual and interactive demo are available by clicking this link: <http://www.ecog.org/general/stsinfo.html>

Please take a moment to familiarize yourself with the software prior to using the system.

An STS generated shipping manifest form should be shipped with all specimen submissions.

Please direct your questions or comments pertaining to the STS to
[contact]

Generic Specimen Submission Form (#2981v3) will be required only if STS is unavailable at time of specimen submission. Notify the laboratory of the shipment by faxing a copy of the completed form to the laboratory.

Retroactively enter all specimen collection and shipping information when STS is available.

